#### **10.4.8. Follow-up and Outcome of AEs**

If possible, AEs will be followed until resolved (synonyms: recovered, recuperated, ended) either with or without sequelae, including for patients who prematurely discontinue study participation. For AEs that are assessed as not drug-related and are not resolved at the EOS visit, follow-up may be limited with the approval of the Medical Monitor.

The outcome of each event will be described using the following categories:

- **Resolved without sequelae** — the event resolved and patient returned to baseline.
- **Resolved with sequelae** — the event resolved but the patient is left with residual problems (e.g., functional deficits, pain).
- **Resolving** — at the last observation, the event was improving.
- **Not Resolved** — at the last observation, the event was unchanged.
- **Death (Fatal)** — to be used for the *one* AE which, in the judgment of the Investigator, was the *primary* cause of death.
- **Unknown** — there were no observations after the onset (initial observation or report) of the event.

Note: Resolving and Not Resolved may also be used for AEs that were unresolved at the time a patient died, but were *not* assessed as the primary cause of death.

#### **10.4.9. Date and Time of Outcome**

For each class of outcome as defined above, [Table-15](#) indicates the date and time to be recorded. As discussed in detail for date/time of onset (see [Section 10.4.2](#)), determining the date/time an event resolved (ended) should reflect the type of event and the source of the information.

**Table-15. Date and Time of Outcome for Adverse Event by Outcome Class**

Outcome assigned to Adverse Event	Date and Time to be Recorded
Resolved (with or without sequelae)	Date and time event observed or reported as resolved
Death	Date and time of death
Resolving or Not Resolved	Date and time of last observation
Unknown	None (see definition above)

## 10.5. Reporting Adverse Events

### 10.5.1. Where to Report SAEs

Serious AE reporting will be performed by the site using the EDC system; detailed training will be provided during site initiation. Reports and supporting materials relating to SAEs will be scanned and uploaded into the EDC system. Contact information for the Medical Monitor and the Pharmacovigilance services is provided in [Table-1](#) and [Table-2](#).

In the event a SAE cannot be submitted via EDC, contact information is provided in [Table-1](#) for alternative submission methods.

### 10.5.2. Procedures for Reporting SAEs to the Sponsor

The **initial notification** of each SAE will be entered into the EDC system **within 24 hours** of the time the Investigator (or the Investigator's designee) becomes aware that the event has occurred. The following items will be entered into the appropriate EDC section (any items not available should be explicitly noted):

- Protocol number, study site, patient number.
- Investigator's name and contact information (phone, email).
- Description of the event (i.e., date and time of onset, initial assessment, treatments and course).
- Current status of the patient and the event.
- Criteria by which the event was assessed as serious.
- Date of the first injection of study drug.
- Date of the last injection of study drug prior to the event.
- Assessment of relationship of study drug to the event.
- Whether the study drug was discontinued or adjusted as a result of the event.

The following **additional** information will be entered within 2 days for death and life-threatening events and within 4 days for all other SAEs;

- Narrative summary of the event — to include specific information that will assist in understanding the event, e.g., relevant medical history, co-morbid conditions, physical exam, diagnostics, assessment, treatments (including concomitant medications), response to treatment, course, and outcome (if known);
- Copies of relevant medical reports — including diagnostic procedures (e.g., laboratory, ECG, x-ray), surgical procedures, and consultations.

Additional documentation may be submitted as part of a follow-up report.

### ***10.5.3. Other Reportable Events***

Certain events that occur in the absence of an AE should be reported to the Sponsor. These include the following:

- Pregnancy exposure (patient becomes pregnant while taking study drug). Should a female patient or partner of a male patient become pregnant during the study, the patient will inform the Investigator. The patient will be asked to follow up with the study site to report the eventual outcome of the pregnancy. The information will be tracked by the Sponsor.
- Lactation exposure (patient was taking study drug while nursing an infant).
- Accidental exposure (someone other than the patient was exposed to study drug).
- Overdose (patient received more than the prescribed dose of study drug within a given timeframe).
- Other medication errors that potentially place patients at greater risk of harm than was previously known or recognized (e.g., study drug was administered via incorrect route).

### ***10.5.4. Requirements for Expedited and Periodic Reporting of Adverse Events***

Suspected unexpected serious adverse reactions are required to be reported rapidly to regulatory authorities and to IRBs (typically within 7 days for fatal or life-threatening SUSARs; within 14 days for all other SUSARs). The Sponsor and the Investigator will work together to meet these reporting requirements.

### ***10.5.5. Notification of SAEs to the Investigator by the Sponsor***

In accordance with regulatory requirements, the Sponsor or designee will notify the Investigator of the occurrence of SUSARs reported by other Investigators in this or in other studies involving the study drug. The Investigator will promptly inform his/her IRB of such communications from the Sponsor and will document that notification in the Investigator's Regulatory Binder.

## 11. DATA QUALITY ASSURANCE

### 11.1. Compliance

The Sponsor and the Investigator will conduct the study in accordance with:

- The protocol — as approved by applicable regulatory authorities;
- Ethical standards and procedures — as detailed in [Section 13](#);
- “Good Clinical Practices” and “Good Manufacturing Practices” — as detailed in documents issued by the International Council for Harmonisation (ICH);
- Applicable national regulations — e.g., in the US, 21 Code of Federal Regulations (CFR).
- FDA guidance document: Safety Reporting Requirements for INDs and BA/BE Studies

### 11.2. Training and Qualifications of Site Personnel

All site personnel involved in the study will be trained regarding the protocol and the study drug. This includes, but is not limited to, pharmacy, nursing and medical personnel involved in handling and administering the study drug, monitoring the patients and collecting clinical data.

The Sponsor (or designee) will provide formal training sessions either off-site (e.g., Investigators Meeting) or on-site (e.g., site initiation visit). Topics covered will include, but not be limited to, background of the investigational drug, the protocol, study events, study procedures, data collection and recording, expedited and routine reporting of AEs, and regulatory requirements. It is the responsibility of the Investigator to document that all participating study personnel have received adequate training.

### 11.3. Source Documents

Source documents are the originals of any documents used by the Investigator, hospital, or institution that verify the existence of the patient and substantiate the integrity of the data collected during the trial. Medical records related to the patient’s routine clinical care, including prior to or during the study:

- Information obtained from the patient’s personal physicians or other third parties regarding the patient’s medical history or prior physical condition.
- Medication prescription and administration records.
- Laboratory reports, including clinical pathology and diagnostic histologic pathology.
- Reports of imaging studies.
- Data and reports from automated instruments (e.g., ECGs, cardiac monitors, vital signs).
- Medical records relating to scheduled and unscheduled clinical visits.

It is expected that Investigator's clinical practice will include medical records that meet current best practices for readability and documentation. Electronic health record (EHR) systems should meet current regulatory requirements for "protected health information," including, at a minimum, security requirements for electronic signature and audit trails for changes.

### ***11.3.1. Study-Specific Source Documents***

Study-specific source documents include, but are not limited to, the following:

- The ICF, signed and dated by the patient.
- The site screening log.
- Any clinical reports noted above that are scheduled as part of the protocol and have been annotated to indicate the significance of any abnormal findings (see [Section 10.4.5](#)).
- Concomitant medication prescription and administration records.
- Records relating to scheduled and unscheduled study visits, including, but not limited to, results of examinations, observations relating to AEs, and concomitant medications.

Study-specific source documents must meet the following requirements:

- Be prepared at the time of the events or activities described (i.e., contemporaneously);
- Indicate both the date and time recorded;
- Identify the source of all recorded information (e.g., the patient, direct observations of the recorder, lab reports, external / historical sources);
- Text should be readable and unambiguous, including application of best medical record practices (e.g., minimal use of abbreviations; proper numerical, dose and posology formats);
- Entries will be signed and dated by the recorder.

Study-specific paper documents must meet the following additional requirements:

- Be written legibly in dark (preferably black) ink, including signature and date;
- In the event that any entry needs to be changed, a single line will be made through the original entry, the correct information added next to it, and the action initialed, dated, and explained (if appropriate). The original entry must not be obscured or obliterated by multiple cross-out, correction fluid or overlay of other material.

Study-specific source document forms created by the site must be reviewed by the Sponsor prior to use.

### ***11.4. Electronic Case Report Forms***

The Sponsor will provide a regulatory-compliant EDC system for reporting study data to a central facility holding the trial database. All study personnel will be trained on the system and each will have a unique login password and electronic signature.

The Investigator (or qualified sub-Investigator approved by the Sponsor) will review all eCRFs and indicate their concurrence by (electronic) signature.

### **11.5. Protocol Deviations**

A protocol deviation is defined as an event in which the Investigator or site personnel did not conduct the study according to the Protocol, including compliance requirements and agreements. Guidelines for minor procedural variations (e.g., collection time of blood samples) will be agreed to and documented by the Investigator and the Sponsor prior to starting the study. Events conforming to those guidelines will not be considered deviations.

For protocol deviations relating to individual patients, the event and relevant circumstances will be recorded on source documents and on the appropriate eCRF; reported to the Sponsor in a timely manner; and presented in the Clinical Study Report (CSR).

Deviations that are not patient-specific (e.g., unauthorized use of an investigational agent outside the protocol, either human administration or laboratory use) will be reported to the Sponsor in writing and copies placed in the Trial Master File (TMF).

Deviations that can be anticipated should, if possible, be discussed with the Sponsor before being implemented.

### **11.6. External Review of the Study Conduct at Participating Sites**

All study-related materials at the site are subject to external review to ensure the safety of the patients, the integrity of the study data, and compliance with all applicable regulatory and oversight requirements.

There are several different classes of review:

- Monitoring — review by the Sponsor or authorized representatives, typically from the contract research organization (CRO) coordinating the clinical conduct of the trial. As detailed below, visits may be conducted before, during, and after the conduct of the study.
- Audits — systematic, independent review by the quality assurance department of the Sponsor or authorized representatives, potentially from an organization not involved in the clinical conduct of the study;
- Regulatory review — performed by representatives of regulatory authorities with responsibility for oversight of the trial or approval of the investigational agent. These authorities may be from the country where the site is located or from another country.

Monitoring and auditing visits on behalf of the Sponsor will be scheduled with the Investigator in advance and will be conducted at a reasonable time. To facilitate these visits, the Investigator will assure that the following are available:

- Appropriate space, facilities and access to all source documents (including access to computerized records either electronically or as complete print outs).
- Consent forms, eCRFs, SAE forms, and medical records for all screened and enrolled patients.

- Timely access to site personnel, including the Investigator, sub-Investigator(s), and other study personnel on the day of the visit to resolve any questions that arise.

Regulatory authorities may visit and review the site and/or Investigator during or after the study and may or may not notify the Investigator or the Sponsor in advance. The Investigator will fully cooperate with regulatory audits conducted at a reasonable time in a reasonable manner. The Investigator will notify the Sponsor immediately of any contact by or communication from regulatory authorities regarding the study.

## **11.7. Study Monitoring Visits**

### ***11.7.1. Site Qualification and Initiation Visits***

Before an investigational site can enter a patient into the study, a representative of Idera Pharmaceuticals, Inc. will visit the site to perform the following:

- Inspect the facilities (e.g., clinical and administrative areas, pharmacy, laboratory).
- Discuss with the Investigator(s) and other personnel their responsibilities with regard to protocol adherence, as well as the responsibilities of Idera Pharmaceuticals, Inc. and its representatives.
- Review the site TMF, including documentation related to the protocol, the Investigator, and other study site personnel; correspondence to and from the IRB, the Sponsor, and their representatives.
- Review the standard operating procedures and current practices relating to clinical and pharmacy activities, data handling, the IRB oversight and the informed consent process.

### ***11.7.2. Interim Monitoring Visits***

During the study, a monitor from or representing Idera Pharmaceuticals, Inc. will visit the investigational site, for the following:

- Provide information and support to the Investigator(s).
- Confirm that facilities remain acceptable.
- Confirm that the investigational team is adhering to the protocol, that data are being accurately recorded in the case report forms, and that investigational product is being appropriately handled and accounted for.
- Perform source data verification, including verifying the data in the eCRFs against the relevant source documents (see [Section 11.3](#)) and resolving any discrepancies noted.
- Record and report any protocol deviations.
- Confirm that AEs and SAEs have been properly documented on eCRFs; that any SAEs have been forwarded to Idera Pharmaceuticals, Inc.; and that SAEs meeting criteria for reporting have been forwarded to the IRB.

Between visits the monitor will be available as needed to provide information or support to the Investigator(s) or other staff.

### **11.7.3. *Study Closeout Visit***

The study will be considered complete when all of the following have occurred:

- All treated patients have completed all scheduled visits plus any unscheduled follow-up required by AEs;
- All eCRFs have been completed, submitted and all queries resolved;
- The trial database has been locked.

The Sponsor or designee will then conduct a study closeout visit, which may include, but is not limited to, the following:

- Review the site TMF to assure all required regulatory documents are current and complete.
- Resolve any open issues from prior monitoring, audit or inspection visits.
- Review the site's provisions for meeting the requirements for retention study records.
- Discuss possible future site audits.
- Review the Sponsor's publication policy.
- Confirm compliance with requirements for notifying the IRB of study events, including closure.
- Collect any unused study materials for either return to the Sponsor or disposal in a manner approved by the Sponsor.

## **11.8. *Resolution of Deficiencies***

The Investigator agrees to take promptly any reasonable steps requested by the Sponsor to resolve any deficiencies identified as a result of monitoring, audits, inspections, protocol deviations, or review of any other study documentation. Failure to take adequate remedial action can result in suspension or termination of the study at the site.

## **11.9. *Retention of Records***

All study-related materials at the site (e.g., source documents, eCRFs, TMF) will be retained according to ICH guidelines and applicable regulations.

The study drug is being developed under a US Investigational New Drug application; regulations require all study-related materials be retained for ***at least 2 years after*** one of the following events:

- Approval of a New Drug Application based on this study.
- Notification by the Sponsor that no further application will be filed.

The Investigator will use the following procedures regarding retained records:

- Contact the Sponsor *before* destructing any records pertaining to the study.
- Provide the Sponsor an opportunity to collect the records.
- Obtain written permission from the Sponsor to destroy the records.
- Notify the Sponsor if the Investigator plans to leave the institution so that arrangements can be made for the transfer of records.

Clinical and laboratory samples that are unstable may be disposed with the written approval of the Sponsor.

#### **11.10. Data Management**

A detailed Data Management Plan will be prepared separately and approved by the Sponsor.

## 12. STATISTICS

The sections below indicate the overall structure and approach to the analysis of this study. A detailed Statistical Analysis Plan (SAP) incorporating these sections below will be prepared separately and approved by the Sponsor. The SAP will define populations for analysis, outline all data handling conventions, including software, and specify additional statistical methods to be used for analysis of safety, efficacy, and PK.

### 12.1. Sample Size Determination and Study Power

Following identification of the MTD/RP2D, up to an additional 22 patients will be enrolled at the MTD or proposed RP2D level. With a total sample size of 22 patients, there is a 90% probability to detect an AE with a true incidence rate of 10%. A secondary objective of this study is to determine the treatment effect of IMO-8400 in patients enrolled at the MTD/RP2D. Using the exact binomial distribution with a 1-sided test and an alpha of 0.05, there is 79% power to detect a response rate of 33% as compared to a null response rate of 10%.

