## 1.8. Statistical Methods

Safety observations will be analyzed using descriptive statistics and tabulation.

Following identification of the MTD/RP2D, up to an additional 22 patients will be enrolled at the MTD or proposed RP2D level. With a total sample size of 22 patients, there is a 90% probability to detect an AE with a true incidence rate of 10%. A secondary objective of this study is to determine the treatment effect of IMO-8400 in patients enrolled at the MTD/RP2D. Using the exact binomial distribution with a 1-sided test and an alpha of 0.05, there is 79% power to detect a response rate of 33% as compared to a null response rate of 10%.

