### 6.2. Dose-escalation Cohorts

The dose escalation cohorts (3 to 6 patients each) will systematically evaluate the safety and tolerability of IMO-8400 at increasing dose levels in order to identify the MTD/recommended Phase 2 dose (RP2D).

- The planned dose escalation cohort levels for IMO-8400 are 0.6, 1.2, 2.4, and 3.6 mg/kg administered once weekly and 1.2 mg/kg administered twice weekly ([Table-8](#)). Additional dose levels, schedules, and routes of administration may be evaluated based upon the emerging data. Weekly exposure is based on body weight (see [Section 8.1](#) for details). Doses will be administered by SC injection.
- For Dose Level 3 (refer to [Table-8](#)), the total dose will be divided into 2 equal portions (1.2 mg/kg twice weekly), administered as separate SC injections over the course of the week, preferably 72 to 96 hours apart (minimum 48 hours) (see [Section 8.4](#) for details).
- Once safety has been established for the 2.4 mg/kg/week as a divided weekly dose (1.2 mg/kg twice weekly), the same dose level of 2.4 mg/kg/week and subsequent dose levels will be given as a once weekly administration.
- Once the RP2D/MTD has been established, patients being treated at lower dose levels may have their doses escalated to the RP2D/MTD upon discussion and agreement between the Sponsor and the Investigator.

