### **6.3.2. *Definition of Maximum Tolerated Dose and Recommended Phase 2 Dose***

The MTD is the highest dose level meeting *both* of the following criteria:

- It is below the level at which 2 or more patients experienced DLTs during the first 4 weeks of treatment;
- It is a dose level at which no more than 1 patient experienced DLTs during the first 4 weeks of treatment.

The RP2D will be a dose at or below the MTD based on clinical data.

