### **6.3.3. *Dose-escalation Enrollment and Review***

Each dose-escalation cohort is expected to enroll at least 3 patients, with a maximum of 6.

- If the initial 3 patients all complete 4 weeks of treatment without a DLT event, the DRC will conduct a dose-escalation review.
- If 1 of the initial 3 patients experiences a DLT event prior to completing 4 weeks of treatment, then enrollment at that dose level will continue to a total of 6 patients and the dose-escalation review will be done when all 6 patients have completed 4 weeks treatment.
- If 2 patients at a dose level experience DLT events during the first 4 weeks of treatment, then no further patients will be enrolled until the DRC completes a review, which should be done as soon as feasible.

Once the last patient in a given cohort has a completed 4 weeks of study treatment, a DRC meeting will be convened to review all safety data and to decide whether to continue or halt dose escalation, or explore intermediate dose levels. To facilitate standardizing the dose-escalation reviews across different cohorts, the focus will be on observations from the first 4 weeks of treatment at that dose level.

The following represent anticipated outcomes for the review process (refer to DRC Charter for full details):

- Dose escalation – progression to the next planned dose level.
- Continue cohort enrollment (applicable only to review after 3 patients) – enroll up to 6 patients at the current dose level to obtain additional safety data for subsequent review.
- Dose de-escalation – enrollment of intermediate dose levels for exploration of other schedules of administration (see [Section 6.5.2](#)).
- Approve enrollment in an expansion cohort at a selected dose level, if applicable (see [Section 6.4](#)).
- No further dose escalation enrollment – at this time the DRC will indicate the dose level that they consider represents the MTD.

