## 6.4. Expansion Cohorts

The expansion cohorts provide for additional enrollment at agreed upon dose levels to assess the dose dependence of clinical response.

Once the MTD or a potential RP2D and/or schedule have been established during dose escalation, up to 22 patients will be treated at the RP2D level according to this schedule. The Sponsor may decide at any point during the expansion phase to modify the RP2D based on emerging data including, but not limited to, safety, DLTs, PK, and clinical activity. If such a change is made, enrollment may continue at the selected dose level in up to 22 patients.

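### Does calling the 22 expansion patients both additional and the total leave the response test without a defined group?

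*Protocol*

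**What the plan says.** Section 12.1 says that, once the dose is identified, "up to an additional 22 patients will be enrolled at the MTD or proposed RP2D level. With a total sample size of 22 patients" the probability of detecting an adverse event of 10% incidence is 90%. Synopsis section 1.8 repeats the phrase: "With a total sample size of 22 patients". Section 12.1 continues: "A secondary objective of this study is to determine the treatment effect of IMO-8400 in patients enrolled at the MTD/RP2D". It gives 79% power for an exact binomial test, one-sided at 0.05, of a 33% response rate against a null of 10%.

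Three other places bear on who is at that dose:

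- Section 6.2 sets the escalation cohorts: "The dose escalation cohorts (3 to 6 patients each"). It also says that, once the dose is established, "patients being treated at lower dose levels may have their doses escalated to the RP2D/MTD".
- Section 6.3.2 says: "The RP2D will be a dose at or below the MTD based on clinical data".
- Section 6.4 describes the expansion as further enrolment of up to 22 patients at the RP2D. It lets the sponsor modify the RP2D during expansion: "If such a change is made, enrollment may continue at the selected dose level in up to 22 patients".

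Section 12 states that the SAP will define the analysis populations and add statistical methods for efficacy.

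**The concern.** If 22 patients are additional to an escalation cohort of 3 to 6, the total at that dose is 25 to 28. The same number cannot be both the addition and the total. The response objective refers to everyone enrolled at the MTD/RP2D, which read literally takes in the escalation patients.

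Two things could depend on the reading.

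- **The result.** Five responders among 22 new patients fail (p = 0.062). If one of three escalation patients also responded, six of 25 would pass (p = 0.033). In the other direction, six of 22 pass (p = 0.018), but six of 28 fail (p = 0.055).
- **The error rate.** The RP2D is chosen on clinical data. Counting escalation patients would re-use responses that may have helped to choose the dose.

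A change of RP2D during expansion would also leave two groups that could each be described as enrolled at the RP2D.

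**Working it through.** **Inputs.** Null rate 0.10, alternative 0.33, one-sided alpha 0.05, n = 22, stated power 79%, adverse-event incidence 0.10 with stated detection 90% (all section 12.1). Escalation cohort 3 to 6 (sections 6.2 and 6.3.3).

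**Formulas.** The critical value c(n) is the smallest c with P(X ≥ c | n, 0.10) ≤ 0.05. Power is P(X ≥ c(n) | n, 0.33). Detection is 1 − 0.9^n.

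**The plan's own figures, n = 22.**

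- P(X ≥ 5 | 22, 0.10) = 0.062, above 0.05. P(X ≥ 6 | 22, 0.10) = 0.018. So c = 6.
- Power = P(X ≥ 6 | 22, 0.33) = 78.4%. With one third in place of 0.33 it is 79.4%. The stated 79% is reproduced.
- Detection = 1 − 0.9^22 = 90.2%. The stated 90% is reproduced.

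**If the escalation patients were added.**

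| n | c | size | power at 0.33 | detection |
|---|---|---|---|---|
| 22 | 6 | 0.018 | 78.4% | 90.2% |
| 25 | 6 | 0.033 | 88.1% | 92.8% |
| 26 | 6 | 0.040 | 90.4% | 93.5% |
| 27 | 6 | 0.047 | 92.3% | 94.2% |
| 28 | 7 | 0.018 | 86.6% | 94.8% |

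No pooled row is near 79%. Among smaller samples, n = 19 comes close on power (80.4%), but its detection is 86.5%. Only 22 fits both stated figures.

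**Who the 22 are.** Power depends on the number of patients, not on when they enrolled. A total of 22 made up of 16 to 19 new and 3 to 6 escalation patients would give the same 78.4%. The text has to decide this. Section 12.1 calls the 22 additional, the next sentence refers back to them, and section 6.4 describes the expansion as added enrolment of up to 22. The overall figure of approximately 60 (section 6.7) points weakly the same way: five levels of at most 6 give 30, and 30 + 22 = 52 is nearer to 60 than 30 + 16 = 46.

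**Error rate if patients were pooled after selection.** Suppose the true rate is 10% at all five levels, the level with most responses is always chosen, and its m escalation patients are then counted. Let K be the largest of five independent Bin(m, 0.10) counts. False success is the sum over k of P(K = k) × P(Bin(22, 0.10) ≥ c(22 + m) − k). For m = 3, 4, 5, 6 this is 6.9%, 8.7%, 10.6% and 4.7%. With the 22 new patients alone it is 1.8%, whichever level is chosen.

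**The case for a change.** The best case for acting is that this is more than missing detail. The protocol gives one number two incompatible labels, and the SAP is meant to incorporate the section, so it could carry the conflict forward. Section 12.4.1.2 analyses the secondary treatment-effect parameters across all cohorts and by dose level, which would naturally group escalation and expansion patients. Section 4.4.1 reports 3 responders among 6 evaluable patients at 2.4 mg/kg, so some responses are already known. If such a level became the RP2D and those six were counted, success would need only 4 responders among the 22 new patients, which has probability 17.2% at a true rate of 10%. Two sentences would remove the doubt.

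Some of this stands. The wording is imprecise, and counting known responses would be poor practice. But each harmful figure needs a step that the protocol does not plan.

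- No section says that escalation patients enter the test. The grouping in section 12.4.1.2 concerns secondary parameters, not the 10% versus 33% test.
- The selection figures also need the dose to be chosen purely on response, whereas section 6.3.2 caps the RP2D at an MTD defined by toxicity. Even then, six per level gives 4.7%, inside the stated 0.05.
- The 17.2% is conditional on a particular earlier result and is not the error rate of the test.
- A pass on the new 22 becomes a failure on 28 only with exactly six responders among the 22 and none among the six escalation patients. At 25 to 27 the cutoff is still 6, so a pass cannot be lost. Failures can become passes, but again only by pooling.

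The range of 25 to 28 is itself uncertain. Section 4.4.1 reports 19 treated patients, 11 of them at the two lower doses. If those 11 are all who were treated there, 19 − 11 = 8 were at 2.4 mg/kg/week. The pool would then be 30 (cutoff 7, power 91.0%), still far from 79%.

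**Conclusion.** No change to the plan follows. The 79% and the 90% are both correct for 22 patients. On the natural reading, those are the 22 expansion patients named in the preceding clause, and the test on them has size 0.018. The word *total* is a clerical slip and alters no figure.

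What remains open is ordinary SAP content: naming the test set, applying the exact cutoff to the number actually analysed, showing separately the escalation patients and those moved up from lower levels, and handling a changed RP2D. The exact test at 0.05 fixes the cutoff once n is known, and section 6.4 again allows up to 22 patients at a newly selected level.

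The conclusion assumes that the test uses newly enrolled patients, which the wording supports but the power figure alone cannot prove. It also gives weight to the test's role: it serves a secondary objective, and section 6.10.1 presents the expansion as preliminary signal-seeking.
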